1. LAY SUMMARY

Peripheral vascular disease (PVD) and diabetes can lead to various complications in affected people, and they include (diabetic) foot ulcers. Foot ulcers carry with it high levels of morbidity and can lead to further complications such as infection in the ulcer and amputation of the foot. If a foot ulcer develops, it is important to treat it appropriately in order to optimise the chance of the foot ulcer healing and minimise the risk of infection, respectively. The application of dressings and so-called offloading of the foot ulcer area reduces the strain on the wound area and keeps it clean. To allow optimal healing of the wound, it is essential to have sufficiently high oxygen levels. Lack of it, hypoxia, can lead to necrosis and deterioration of the wound. Oxygen promotes the formation of new blood vessels and subsequently the growth of new skin.

New treatment modalities have been introduced to increase oxygen levels in wounds, including hyperbaric oxygen (HBO) treatment. However, such treatments tend to be cumbersome, time-intensive and costly. In the UK, InFirst Ltd has brought to market a new medical device for oxygen treatment, which is designed to be more straightforward to apply than HBO. The product, Granulox, contains porcine haemoglobin contained in a spray canister. It is applied twice weekly to a wound during redressing, ie including foot ulcers, and can be used in a clinic or patient's home setting. Initial case series and retrospective comparative studies have shown that Granulox reduces the time for a foot ulcer to heal.

This study seeks to assess if Granulox has a significant positive impact on the rate of wound healing in foot ulcers. For the first time, a prospective randomised approach is taken, which is a scientifically more solid approach than the case series published to date. This means that by virtue of a computer deciding the type of treatment, participants will receive standard care or standard care plus Granulox spray twice weekly for up to 12 weeks or until the foot ulcer is healed. The effects of the trial treatment on participants' quality of life and its safety will also be appraised.

2. INTRODUCTION

The occurrence of foot ulcers has enormous cost complications. Figures available for diabetic foot ulcer (DFU) alone total £650 million per year once associated morbidity is taken into account (NHS Diabetes report). Non-healing ulcers may lead to bacterial infection of wounds and increase the risk of further degenerative complications including cellulitis, necrotising fasciitis, and sepsis (Grothier, 2015). Specific wounds, again including diabetic foot ulcers, may lead to amputation if osteomyelitis develops. An additional undesirable effect of infected wounds is that it delays – or stops altogether – the wound healing process (Halbert et al, 1992). Therefore, enhancement of foot ulcer healing rate is desirable to minimise morbidity and healthcare costs. Table 1 shows annual NHS cost for treating DFUs compared to other chronic wound treatments. Other foot ulcers are commonly caused by venous insufficiency, and therefore the cost of managing them falls within the venous leg ulcer category of Table 1.

Table 1. Chronic wound treatment costs to the NHS (Posnett & Franks 2008)

[figure not shown]
	Annual Incidence	Cost per patient	Annual NHS cost (2005–2006)
Venous leguicers	108,600	£1,500-1,800	£168-198m
Foot ulcers	57,000	£5,200	£300m
Pressure ulcers	410,000	£4,300-6,400	£1.8-2.6bn
TOTAL	575,600	£4,000-5,400	£2.3-3.1bn

To further illustrate the point concerning the impact of foot ulcers: the healing rate of DFUs is poor; on average, 24% of wounds have healed by week 12 of treatment, and only 31% at 20 weeks of treatment (Margolis, 1999). A cohort study involving 31 diabetic patients determined that the average healing time for neuropathic DFUs is 78 days whereas this increases to 133 days for patients with additional peripheral vascular disease (Zimny et al, 2002). Further analysis has shown that the size of the ulcer negatively correlates to the healing rate, whereas a patient's age, sex, or type of diabetes is not associated with a change in healing rate outcome (Oyibo, 2001). DFU healing progress at 4 weeks of treatment is a predictor of the likelihood that the wound will be healed by 12 weeks of treatment. If the wound has not healed by at least 50% after 4 weeks, the likelihood that the DFU will be completely healed by 12 weeks is reduced to circa 10% (Sheehan, 2003). Taken together, there is a major group of patients with DFU -those with larger ulcers, and co-morbidities, responding poorly to standard treatment in the first 4 weeks – that is at risk of ending up with long-term wounds taking over 3 months to heal, if at all.

Oxygen is an essential component of the wound healing process (Hunt et al, 1969). Poor circulation due to diabetic angiopathy impairs the healing process and limits the degree of required growth factor release and angiogenesis (Falanga, 2005; Mathieu et al, 2006). Increasing oxygen levels can be achieved in various ways, including hyperbaric chamber treatment (Faglia, 1996). However, this method is costly, cumbersome and logistically challenging. A novel haemoglobin spray that is designed to enhance wound healing, including non-diabetic foot ulcers and DFUs, by enriching the wound area with oxygen using porcine haemoglobin is now available in the UK. The product is called Granulox and it marketed by InFirst Healthcare Ltd. The mode of action is the application of porcine haemoglobin onto a wound to facilitate increase oxygen levels through diffusion into the wound area (Arenberger et al, 2011; Norris, 2014; Hunt & Elg, 2016). Hunt & Elg, in a study with retrospective analysis of standard care DFUs and prospective assessment of Granulox adjunct therapy DFUs, have shown that the healing rate for chronic wounds is much accelerated with haemoglobin treatment. Figure 1 summarises their data.

The aim of this randomised, controlled, prospective clinical trial is to determine the efficacy of the Granulox haemoglobin spray device as an adjuvant therapy for foot ulcers, with a primary outcome measure of DFU healing at 12 weeks of treatment. The rationale behind including both diabetic and non-diabetic foot wounds is that the mechanism of action of Granulox is not affected by a patient's diabetes status and the product has shown promise in non-diabetic wounds (Arenberger et al, 2011).

Figure 1, Hunt & Elg data, DFU healing by week vs baseline.

3. INVESTIGATIONAL DEVICE

Granulox® Medical device. Class III, CE 0482

Indications: Granulox® is a spray for use on chronic wounds. Granulox® is an innovative medical device for the proposed treatment of chronic wounds, such as venous leg ulcer, arterial leg ulcer, mixed leg ulcer, diabetic foot ulcers, secondary healing of surgical wounds and pressure sores. Granulox® can also be used on sloughy and infected wounds. Each canister contains 12 ml of spray, sufficient for 30 wound treatments.

Medical Device management

The Granulox devices, ie the individual canisters, will be stored and used in line with published guidelines. Link: http://www.woundcarehandbook.com/product/2736/granulox. The stock of Granulox devices will be registered on a device log and given a local ID. Each time a canister is issued / used, this is updated on the device log. Each participant will have their own Granulox canister, to avoid any risk of cross-contamination.

A temperature-monitored refrigerator will be used for storage of the devices. The temperature will be recorded every day. Once a patient is recruited and they are treated on location - eg a community clinic away from where the pharmacy department is located, then the canister will be stored in a lockable fridge at the relevant location. These fridges on location will be monitored every 2 weeks since the product can be stored up to 6 weeks at room temperature (< 50°C).

Used canisters will be disposed of in line with local guidelines on disposal of clinical waste.

Figure 2. Granulox device

4. STUDY HYPOTHESIS

4.1 Primary objective

 To assess the efficacy of Granulox haemoglobin spray adjuvant treatment for enhancement of healing of foot ulcers when compared with standard care.

4.2 Secondary objective

 To assess any changes observed in clinical assessments, safety of Granulox, and patient-reported outcomes related to foot ulcers (including pain, mobility, quality of life)

5. STUDY PROTOCOL

5.1 Study design and timeline

This concerns a single centre, controlled prospective randomized study. The study will be carried out in Cumbria by NHS Cumbria Partnership NHS Foundation Trust. The study will take place in a local community setting with support and oversight from a GP, podiatrists and research staff. Research delivery staff will be delegated to provide support with data collection and processing.

Table 2. Anticipated timeline

Month	Setup	Recruitment	Analysis	Finalise
June-17	Submission for			
	HRA approval			
July-17	NIHR portfolio			
	adoption			
Aug-17	HRA and Trust	Start recruitment		
	approval			A REMARKS AND THE
Jan-19		Finish recruitment		
Apr-19			Follow-up	
			complete;	
			🔭 Analyse data .	
May-19				manuscript &
				report writing
The state of the s				complete
				epselite L

5.2 Participant identification and research setting

Participants will be recruited from podiatry clinics and all eligible patients will be invited to take part until the required numbers have been achieved. Identification will be by the podiatrists who are supporting the study. A screening form will be completed for potentially eligible patients to confirm that they indeed meet the trial criteria.

The podiatry team in West Cumbria will be supporting this study, and the study will take place in Whitehaven, Workington, Cockermouth and Wigton. All research activity and also treatment as usual (ie application of dressings) will take place in these clinic settings. Additional resource, paid for by the research grant for this study, means that there is sufficient capacity to treat study participants with the Granulox medical device. All podiatrists – 4 staff in total - will receive training on the use of the medical device by a representative of InFirst Healthcare.

To summarise, the podiatrists will:

- Identify potentially eligible patients and ask verbal consent for them beign approached about the study by a member of the R&D team
- Complete the incl/excl criteria part of the screening form
- Apart from treatment as usual activities (dressings, cleaning of wound, footwear advice), measure the wound size and complete the PUSH and Texas University score once a patient has consented to taking part (informed consent will be taken by members of R&D team, or one of the podiatrist so long as GCP training has been completed).

5.3 Consent

Those eligible will be approached and provided with an information pack and consent form, which will be signed to indicate that informed consent has been given. Patients will be given ample time to consider taking part, more than 24 hours if they wish. The direct healthcare professional will first approach a patient about the study, and after verbal consent by the patient the healthcare professional themselves or a member of the research team can go through the informed consent process.

Patients are also allowed to consent to taking part when first approached as long as the study has been discussed with the patient and they have been given time to read the patient information leaflet and opportunity to ask any questions that they may have. Participants will receive no incentives and consent will be regarded as a process and not a one-off event. Participants are free to withdraw from the study at any time without the need to give any reasons for withdrawal. Their standard of care will not be affected by either declining to participate in the study or withdrawing during participation. Data collected up to the date of withdrawal will be retained for analysis.

5.4 Recruitment

Participants will be randomised to either the control group (TaU) or the intervention group (TaU plus administration of Granulox spray) for 12 weeks or until ulcer healing has been achieved. All participants will have demographic data obtained and the following base line measures (table 2):

- Foot ulcer size measured with Convatec grid tool or equivalent measuring tool
- PUSH score (size and characteristics)
- Texas University grading scores.
- Mobility score (LifeSpace questionnaire)
- Quality of life assessment using
 - o EQ-5D-5L
 - o Cardiff Wound Impact Questionnaire
 - VAS pain scale

Table 3. Overview of measurements

Weeks	-2	0	3	6*	9*	12#	18#
· Ulcar size (Converted grid))	X	Х	X	X	X	X	110-11
PUSH score	Χ	Χ	Χ	Χ	X	Χ	A48.400401-144.1
Tiexas Universading score	X	1X	X	: X	\mathbf{X}_{i}	X	
Wound healed status		Χ	Χ	Х	X	Χ	Χ
Lifte Space Questilonnaire		X		X -		X 14 3	
QoL EQ-5D-5L		Χ		Χ	The state of the s	Χ	
QoL CWIQ ************************************	Angel bir sho	1 X 1	orași d	14X1		· XD a	
VAS pain scale	X	Χ	Χ	Χ	Χ	Χ	
Patient experience questionnaire	richt sach Richer Ha d	26021	dylast.	Brutta.		X [®]	

^{*} Allowed to be up to 1 week early or late

[#] Allowed to be up to 2 weeks early or late

@Granulox arm participants only

The Pressure Ulcer Scale for Healing (PUSH) tool, see Appendix 1 is a standardised method of assessing and monitoring the severity and healing of both pressure ulcers and venous leg ulcers (Stotts et al, 2001; Ratliff & Rodeheaver 2005). The Pressure Ulcer Scale for Healing (PUSH) is a valid, responsive, evaluative tool to monitor and document wound progress of foot ulcers (Hon, 2010). Findings also suggest that total PUSH scores predict time-to-heal for foot ulcers (Gardner 2011).

A mobility measure will be taken using a life space questionnaire, see Appendix 1 (Stalvey *et al* 1999). This is a tool that has demonstrated reliability and construct and criterion validity in establishing the spatial extent of an older person's mobility within their home setting. There are other versions (Peel *et al* 2005) that additionally measure the use of aids and equipment however this is not of particular interest within the study, hence the simpler version will be used.

A recent review of specific health related quality of life instruments for venous leg ulcers favours the Charing Cross Venous Leg Ulcer Questionnaire (Appendix 2) (Smith *et al* 2010) above others such as the Hyland for its disease specific psychometric characteristics (Gonzalez & Verdu 2011).

5.5 **Follow-up**

Patients are in the study for a period of 18 weeks. Thereafter, the patient will be followed up as they would be in normal clinical practice. During and after the trial, clinical staff will redress the wound as per routine care, and during the trial they will conduct the measurement of the foot ulcer (grid measurement tool, Texas Univ grading and PUSH score). The researcher will be in attendance at -2 weeks, 0 weeks, and weeks 3,6,9,12 of study participation to randomise the patient, issue the Granulox spray if indicated, and conduct/collect the study participant questionnaires. The researcher will phone the participant at week 18 to check on wound status and any adverse event reporting.

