HAWS; Haemoglobin Application to Wounds Study, a single-centre, controlled, prospective randomized trial

Version 6, dd 10July 2018

Chief Investigator's Statement of Ownership and Content.

I, [name], confirm that this protocol is my work and is owned by me. The protocol conforms with standards outlined in the Declaration of Helsinki 1964.

Name (PRINT): [name]

Signature:

Date: LATH SEP. 2018

RESEARCH PROTOCOL SUMMARY

TITLE:	Haemoglobin Application to Wounds Study, a single-centre, controlled, prospective, randomized trial of Granulox
	haemoglobin spray for adjuvant treatment of foot ulcers
Short title:	HAWS; Haemoglobin Application to Wounds Study
IRAS number	227421
Device description	Granulox® Medical device. Class III, CE 0482
	Indications: Granulox® is a spray for use on chronic wounds. Granulox® is an innovative medical device for the proposed treatment of chronic wounds, such as venous leg ulcer, arterial leg ulcer, mixed leg ulcer, foot ulcers, secondary healing of surgical wounds and pressure sores. Granulox® can also be used on sloughy and infected wounds. Each canister contains 12 ml of spray, sufficient for 30 wound treatments.
Study design	Single-centre, controlled, prospective randomized trial
Primary objective	To determine the efficacy of the Granulox spray as an adjuvant therapy for foot ulcers at 3, 6, 9 and 12 weeks post-baseline - Healing rate (ulcer size; 12 weeks is endpoint for power calculation), as measured with surface area scoring grid
Secondary objectives	Clinical assessment at -2, 0, 3, 6, 9 and 12 weeks, and - PUSH ulcer size/grading score - Texas Univ grading score - Wound closure Safety of Granulox spray throughout trial duration, up to 12 weeks - Wound infection incidence; secondary interventions Patient-reported outcome measures at 0, 6 and 12 weeks - Patient mobility score (LifeSpace questionnaire) - Quality of life score (EQ-5D-5L and CWIQ) - Visual Analogue Score for pain associated with DFU Status of wound at week 18 - Healed, not healed, recurrence.
Patient population	A total of 60 participants, over the age of eighteen, with measurable foot ulcer, treated in clinic. Forty patients to have a DFU and further 20 patients to have nondiabetes related foot

	Indiana B. III in the second s
	ulcer. Participants must have the capacity to provide informed written consent and complete patient reported outcome measures.

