5.6.2 Secondary outcome measures

This study also aims to record wound characteristics and patient-related outcomes measures, as well as safety endpoints.

- Size and characteristics of foot ulcer, determined with PUSH score (week -2, 0, 3, 6, 9, 12)
- Grading of foot ulcer, using Texas Univ grading score (week -2, 0, 3, 6, 9, 12).
- Wound closure status (week 0, 3, 6, 9, 12)
- Mobility score, as determined by LifeSpace questionnaire (week 0, 6, 12)

- Visual Analogue Pain score (week -2, 0, 3, 6, 9, 12)
- Quality of life score, determined with EQ5D-5L and Charing Cross Venous Ulcer Questionnaire (week 0, 6, 12)
- Wound status check [healed, not healed, recurrence] and any incidences of adverse events (week 18)
- Patient withdrawal rates due to change in management (e.g. need for surgery)
- Wound infection rates, any other adverse events
- Patient experience and satisfaction with the Granulox product and treatment regime

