6.2.1 Inclusion criteria

- Clinical diagnosis of a Foot Ulcer, present on area that is measurable with a grid sheet (this
 can include plantar, calcaneus, dorsal, hallux, apex, or ankle based ulcers). This includes DFU,
 peripheral arterial disease related wound, or other aetiology.
- Foot ulcer present for at least 2 weeks.
- Adult patients aged > 18 years
- Patients with recurrent wounds, including multiple wounds, are eligible. The largest of the wounds, that is measurable with a grid sheet, will be selected for the trial.
- Mental capacity to give consent

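### Week-18 wound status is taken by telephone alone; a check of the clinical record for every patient would firm it up at little cost

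*Protocol*

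**What the plan says.** - **Source at week 18.** Section 5.5: "The researcher will phone the participant at week 18 to check on wound status and any adverse event reporting".
- **Source up to week 12.** Section 5.5 says of clinical staff that "during the trial they will conduct the measurement of the foot ulcer (grid measurement tool, Texas Univ grading and PUSH score". It also says "The researcher will be in attendance at -2 weeks, 0 weeks, and weeks 3,6,9,12 of study participation". Week 18 is not in that list.
- **Status of the outcome.** The summary gives week-18 wound status as a secondary objective with three categories: "Healed, not healed, recurrence". Section 5.6.2 lists "Wound closure status (week 0, 3, 6, 9, 12" as one item and "Wound status check [healed, not healed, recurrence] and any incidences of adverse events (week 18" as another.
- **Schedule.** In Table 3 the grid measurement, PUSH and Texas scores stop at week 12. One healed-status row runs from week 0 to week 18. Weeks 12 and 18 may each be up to two weeks early or late.
- **Treatment and blinding.** Section 5.4 has treatment last 12 weeks or until healing. Section 6.1.1 states that neither participants nor researchers can be blinded and accepts that this raises the risk of bias.
- **Population.** Eligible sites in 6.2.1: "this can include plantar, calcaneus, dorsal, hallux, apex, or ankle based ulcers". The summary plans 40 diabetic foot ulcers among 60 patients. Sections 8.1 and 8.3 record neuropathy.
- **Care after the trial.** Section 5.5: "During and after the trial, clinical staff will redress the wound as per routine care". Nothing makes those staff's findings a source for week-18 status.

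**The concern.** The source of information changes at the point where lasting healing is judged. Recurrence requires an earlier closed state, and that state was established at a clinic visit. The later state is whatever the patient says on the phone. An ulcer that has reopened unnoticed would be recorded as healed. Part of any apparent durability or recurrence could therefore come from the change of source.

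The patient also knows the allocation. A verbal answer leaves more room for expectation than a tracing or a dated clinical note, so errors could differ between arms. What is at stake is one secondary outcome, the last evidence the trial collects on whether closure holds.

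**Working it through.** The protocol states no figure for the week-18 outcome, so there is nothing to reproduce. The check is first a comparison of sections and then an illustration on assumed values.

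**1. The two sources side by side**

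| | Weeks 0 to 12 | Week 18 |
|---|---|---|
| Contact | clinic visit, researcher attending (5.5) | telephone call (5.5) |
| Ulcer measured by staff | yes: grid, PUSH, Texas (5.5, Table 3) | no (Table 3) |
| Patient and researcher blinded | no (6.1.1) | no (6.1.1) |
| Examination, photograph or record check provided for | examination at the visit | none stated |

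The source changes; blinding does not. Section 5.2 places all research activity in the clinics, which the week-18 call does not fit.

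**2. Who depends on the call**

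- Closed at week 3, 6 or 9: treatment has stopped, and Table 3 still schedules clinic checks up to week 12. Early durability is seen in clinic; only the period after week 12 rests on the call.
- First closed at about week 12, or still open then: the call is the only scheduled study check after treatment.

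**3. Is another source available?** Section 5.5 has clinical staff continue redressing after the trial, so an ulcer that is open or has come back to the service should normally have a dated entry. Section 10.2 mentions community nurses seeing patients at home, so that entry may not be a podiatry one. The Table 3 windows give weeks 10 to 14 for the week-12 visit and weeks 16 to 20 for week 18. They do not overlap, so an entry in the second window cannot be the week-12 visit.

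**4. Illustration of misreporting.** Let p be the true proportion healed, Se the chance that a healed ulcer is reported healed, and Sp the chance that an unhealed ulcer is reported unhealed. Then

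observed p = p × Se + (1 − p) × (1 − Sp).

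Take p = 0.24 in controls (the week-12 figure for diabetic foot ulcers in section 2) and p = 0.50 with Granulox. The second value, every Se and Sp, and the use of a week-12 figure at week 18 are assumptions.

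| Se = Sp, both arms | Control observed | Granulox observed | Difference (true 26.0 points) |
|---|---|---|---|
| 0.95 | 0.228 + 0.038 = 0.266 | 0.475 + 0.025 = 0.500 | 23.4 |
| 0.90 | 0.216 + 0.076 = 0.292 | 0.450 + 0.050 = 0.500 | 20.8 |
| 0.80 | 0.192 + 0.152 = 0.344 | 0.400 + 0.100 = 0.500 | 15.6 |

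Now assume no true effect (p = 0.24 in both arms), Se = 0.95 in both, and Sp = 0.95 in controls, so controls show 0.266.

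- Granulox Sp = 0.90: 0.228 + 0.076 = 0.304, a spurious difference of 3.8 points.
- Granulox Sp = 0.80: 0.228 + 0.152 = 0.380, a spurious difference of 11.4 points.

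If the poorer specificity were in the control arm, the sign would reverse.

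**5. Small denominators.** 0.24 × 30 = 7.2, so about 7 controls might be closed by week 12. If 15 were closed with Granulox (assumed), one misreport moves that arm's recurrence proportion by 1/15 = 7 points, and two misreports among 7 controls move theirs by 2/7 = 29 points. This holds for any method of assessment and says nothing about how often misreports occur.

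**The case against.** The strongest case against runs as follows. This is a secondary outcome with no power claim, in a single-centre study with a £6370 grant plus free product, and a phone check is a pragmatic choice. A patient whose ulcer is still being dressed knows it is open, so a closed wound reported as open is unlikely. The plausible error is an unnoticed reopening in someone who no longer attends, and a notes look-up does not reach that patient. Using the record for open ulcers and the phone for closed ones would also tie the source to the outcome.

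Most of this stands. It limits the weight of the point and shapes the fix, but it does not remove the gap: a re-presentation noted by clinical staff and missed on the call would go uncounted.

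A reader might also infer more than the protocol supports:

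- *That all evidence after treatment is self-report.* Patients healed before week 12 have later clinic checks.
- *That many patients cannot see or feel their ulcer.* Sites and neuropathy are mentioned, but no proportion is given.
- *That blinding is lost at week 18.* There is none at any visit.
- *That the plan merges week-18 status with earlier closure.* Table 3 uses one row, but 5.6.2 lists two outcomes, and the comparisons that 8.3 schedules by visit stop at week 12.

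**Conclusion.** The point holds as a modest, inexpensive improvement. The last scheduled wound status comes only from a phone answer by a patient who knows the allocation, whereas earlier status comes from visits where the ulcer is measured. Section 5.5 itself points to a clinical source that the plan leaves unused.

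The size of the error is unknown. The illustrative losses (26 points falling to between 23.4 and 15.6) and spurious differences (3.8 to 11.4 points) rest wholly on assumed accuracy and assumed healing rates. The 7 and 29 points in the last step of the working are small-denominator arithmetic and should not be read as an expected bias. The 12-week ulcer-area endpoint, the sample size and week-12 closure are unaffected.

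**What to change.** In sections 5.5 and 5.6.2:

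1. Keep the week-18 call for all patients.
2. For every patient in both arms, whatever the phone answer, also check the podiatry or community nursing record for the index ulcer within the existing two weeks either side of week 18.
3. Where a dated clinical entry exists, let it take precedence. Record both answers and the source, so that disagreements and the share of phone-only statuses can be shown by arm.
4. Count recurrence only in patients recorded as closed at a study visit up to week 12.
5. Label phone-only statuses as patient-reported and do not merge them with clinic-assessed closure.

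**Cost.** A notes look-up for at most 60 patients, with no added visit or assessor. Checking everyone makes the procedure the same in both arms, but an entry is still more likely when an ulcer is open, which is why the source must be recorded. Healed patients with no clinic contact continue to rely on the call, so unnoticed reopenings in that group should be stated as a limitation.
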